6.4. THE TYPE AND DURATION OF THE FOLLOW-UP OF SUBJECTS AFTER ADVERSE EVENTS

[figure not shown]
All non-mild adverse events (including serious adverse events) should be followed until the event is resolved, stabilized, or until the end of individual's participation in the study. The Site PI or designee will determine a follow-up plan on a case-by-case basis based on their clinical judgment.

6.5. UNBLINDING PROTOCOL

Participants may be unblinded if there is an urgent medical need, as determined by the clinician evaluating the participant. If a participant is unblinded, study medication may be discontinued.

The following are examples of events that may result in emergency unblinding:

- An SAE occurs that is thought to be most likely or definitely related to the study drug.
- An AE or SAE occurs and the clinician treating the patient concludes that knowledge of the treatment arm is necessary to determine the therapy provided to the patient.
- The study drug is accidentally ingested by a child.

6.6. DATA SAFETY AND MONITORING BOARD

The DSMB is responsible for ensuring subject safety (by reviewing blinded and unblinded safety data on a regular basis and assessing the safety of study procedures) and for monitoring the overall conduct of the study. No interim efficacy analyses will be conducted.

The DSMB is an independent group advisory to the PIs and the NIAAA, and is required to provide recommendations about starting, continuing, temporarily suspending the trial until certain conditions are met, and stopping the studies. In addition, the DSMB is asked to make recommendations, as appropriate, about:

- Benefit/risk ratio of procedures and participant burden
- Selection, recruitment, and retention of participants
- Protocol violations and adherence to protocol requirements
- Completeness, quality, and analysis of measurements
- Amendments to the study protocol and consent forms
- Participant safety
- Notification of and referral for abnormal findings

The Board will be composed of three full members (inclusive of the DSMB Chair) and 1 adjunct member.

This DSMB will meet every six months. In cases where Institutional Review Boards or the NIH require more frequent monitoring, procedures will be put into place to conform to those requirements. An agenda will be provided detailing the studies to be discussed. It is estimated that the meeting will be scheduled for 1.5 hours. Each protocol and data review meeting will consist of two sessions: Open Session and Closed Session. Communication in the interim will be as needed. Unscheduled meetings can be requested by any party with the responsibility of overseeing the study. Requests can be made to the DSMB Chair, PIs, or NIAAA officials. The Chair, in collaboration with the Admin Core or NIAAA, will schedule any unplanned meetings.

The DSMB will provide recommendations about temporarily suspending or stopping the study. No interim efficacy or futility analyses are planned because of the risk level of the study and because patient outcomes are very unlikely to be worse in the intervention group in the study. The study team, including the project manager, statistician, co-investigators and research associates, led by the PIs, will evaluate the progress of the study, including periodic assessments of data quality, participant recruitment, accrual and retention, and factors external to the study when interpreting the data, such as scientific developments or the new availability of proven clinical services that could have an impact on the safety of the participants, the performance of the study or the ethics of the study.

7. DATA MANAGEMENT

7.1 DATA COLLECTION

All study data will be captured electronically on netbooks via a secure, web-based data capture system with the exception of: TLFB data and daily pain diaries, which will be collected on paper calendars.

7.2 QUALITY CONTROL PROCESS

Quality control measures will include: detailed and unambiguous specifications for completion of data forms, including rules for coding skipped questions and missing data, training of study staff responsible for data collection and built-in validation rules, error checks, question skips for electronic data capture, and computer algorithms to check for out-of-range codes and internal inconsistencies. All data, regardless of capture method, will be reviewed for logic, skip patterns, response ranges, out-of-range codes, and internal inconsistencies. The RAs will be queried monthly regarding any noted inconsistencies.

7.3 DATA SECURITY AND CONFIDENTIALITY

Screening forms and most other research paperwork will not include the participant's name; instead, a unique ID will be assigned to each person screened, and another number assigned to those who enroll.

Any documents with identifiable participant data will only be accessible to the Russian Co-Investigators, the project manager, and the RAs who recruit and follow participants, and perform QC.

Tracking information will be kept similarly using a Microsoft Excel spreadsheet. The Russian RAs will upload the Excel file to box.com for quality control purposes. Computer data will be password protected, and accessible only to research associates needing the information for follow-up purposes.

Electronic research data will be entered directly into REDCap, which is maintained on secure BU servers. All central systems are secured physically behind two card-access doors with access to the primary door restricted to key personnel. Data will be kept indefinitely. The mastercode will be kept separate from any study data.

7.4 WEB SYSTEMS

The study will use REDCap and Excel. REDCap is a secure web application for building and managing online surveys and databases and will be used for screening and assessments purposes. Excel will be used for participant tracking and scheduling purposes. The study will also use box.com, a HIPAA-compliant, cloud-based content management platform, for quality control purposes. Study forms will be completed according to the schedule below.

FORM	STUDY VISIT							
	Phone Screen	Screen & Baseline Visit		2 week visit	4 week visit	6 week visit	8 week visit	As Needed
		Screen	Baseline					
REDCap								

Pre-Screener	X							
Screener		X						
Consent and enrollment form		X						
Full assessment			X		X		X	
Short assessment (adherence)				X			X	
Baseline Event Form			X					
Medication visit checklist			X		X		X	
Symptom Monitoring Form				X	X	X	X	
Naloxone Challenge Form			X					
Excel								
Contact info		X	X	X	X	X	X	X
Contact log								X
Baseline tracking form			X					
Follow-up tracking form				X	X	X	X	
Participant tracking overview			X	X	X	X	X	
Paper								
Medication collection			X	X	X	X	X	
Study conclusion form								X
AE/SAE form								X

8. STATISTICAL ANALYSIS

This study will use an intent-to-treat analysis that includes all participants according to their randomized assignment. Descriptive statistics will be calculated for variables at baseline and each follow-up time to assess whether there appear to be any differences across treatment arms.

The main focus of this aim is the evaluation of tolerability within each group (naltrexone and nalmefene).

8.1 PRIMARY ANALYSES

Descriptive statistics and graphic displays of all outcome measures will be generated.

The main focus of this aim is the evaluation of tolerability within each treatment group (naltrexone and nalmefene), thus the analysis set will be all participants who receive at least one dose of their assigned intervention. We will report descriptives such as mean tolerability score at 8 weeks within each treatment group along with 95% confidence intervals (CIs). No formal testing will be conducted in this aim. If the data are skewed, transformations will be performed (e.g., log transformation) or the median will be reported if no appropriate transformation is identified. We anticipate that mean tolerability

scores at 8 weeks will not be lower than 80 (this is based on prior study of low-dose naltrexone which reported tolerability scores of 89 in both intervention and placebo). We will also evaluate: 1) mean number of grams of pure ethanol consumed per day, 2) the percentage in each group that discontinue medication during the 8 week treatment period, 3) the mean % adherence to medications in each group, 4) the percentage of participants who report severe or life threatening side effects, or experience hepatotoxicity during treatment and 5) the percentage who say that they would continue the medication if given the option. Corresponding 95% confidence intervals will be reported for each of the above variables. For binary variables, 95% exact binomial confidence intervals (CIs) will be reported.

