2.2 STUDY OUTCOMES

Primary Outcomes: The primary outcome for this study is tolerability of medication during treatment. Based on measurements used by other researchers, medication tolerability will be measured via a 0-100 visual analog scale with 0 anchored as “cannot tolerate at all” and 100 as “tolerate perfectly well.” Participants will be asked to estimated tolerability over the previous 2 weeks at each study visit: the primary outcome will be tolerability score at the week 8 visit.

Secondary Outcomes:

- 1) Alcohol reduction measured as a reduction in mean number of grams of pure ethanol consumed per day.
- 2) Treatment discontinuation: defined as patient self-report of stopping medication anytime during the treatment period. Participants will be instructed to notify the study staff in real-time if they discontinue medications, and they will be queried about discontinuation at the week 4 and 8 study visit assessments. Lost-to-follow-up will be assumed to be equivalent to treatment discontinuation.
- 3) Adherence: defined as self-report of the percentage of study medications taken in the past 2 weeks, using a visual analog scale (VAS) from 0 to 100, same as used to assess adherence to HIV medication. Participants will be asked to mark on the ruler what percentage of medication they have taken that week ("0% means no medication, 50% means half your medication, 100% means all your medication"). In addition, medication adherence will be assessed by Riboflavin (50 mg) that will be included in the capsules by the pharmaceutical laboratory. This allows for assessment of medication adherence in both medication arms. Visual inspection of the urine for the presence or absence of riboflavin using ultraviolet (UV) light at the long wave setting (33 nm) in a room with low ambient light will be conducted.
- 4) Reported side effects. We will use a Symptom Checklist based on side effects reported in prior studies of naltrexone, plus an open-ended question to assess for any side effects from study medications in the past 4 weeks at visits 4 and 8. Participants side effects will be rated by trained research assessors, using the Guidelines for Severity Grades (mild, moderate, severe, and life-threatening, death) (See Box 1).
- 5) Medication Satisfaction: This 14-item questionnaire assesses satisfaction with medication to treat chronic conditions and difficulty/inconvenience of use.

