2.7 RECRUITMENT GOALS

We aim to randomize 16 participants into the trial and a total of up to 30 may be enrolled, but not randomized due to not meeting study entry criteria. Existing Russia ARCH (H-31200) participants will be offered to be screened for PETER PAIN. We will also screen St PETER (H-35288) participants at their final St PETER study visit for eligibility. Recruitment beyond PSMU will occur at local NGOs and Russia ARCH network hospitals including the major clinical HIV hospitals (Botkin Infectious Disease Hospital, Leningrad Regional AIDS Center, St. Petersburg City AIDS Center) and addiction hospitals (Leningrad Regional Center for Addictions, St. Petersburg City Addiction Hospital).

2.7.A. SAMPLE SIZE CALCULATION AND POWER

The goal of this study is to assess the feasibility, tolerability and safety of low-dose naltrexone and standard-dose nalmefene to inform a larger pilot RCT. The study will not be powered to detect statistically significant differences in outcomes and formal statistical testing will not be conducted. If we detect substantial intolerance to medication (mean tolerability rated < 80), and/or if other results qualitatively suggest intolerance (i.e. we have a larger than expected percentage who report discontinuation, non-adherence, side effects, and that they would not want to continue meds), we will not proceed to the next phase (UH3). To illustrate the limits of this phase of study, we provide the width of the CIs for the tolerability outcome within each treatment group. We expect < 15% loss to follow-up at 8 weeks and assume 7 evaluable subjects in each arm. Younger et al. observed a standard deviation of 15.1 for tolerability score. Assuming a similar standard deviation for each arm of this study, the length of a 95% confidence interval for mean tolerability would be approximately 22.4 (e.g., if mean tolerability were 80, the 95% CI would span from 68.8 to 91.2) for either arm.

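### If the week-8 mean is near the cited 89, tolerability scores capped at 100 must be left-skewed: a t interval then under-covers, and the log transformation named in 8.1 makes the skew worse

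*Combined protocol and SAP*

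**What the plan says.** Section 2.2 measures tolerability on a "0-100 visual analog scale with 0 anchored as" not tolerable at all and 100 as perfectly tolerated, and states that "the primary outcome will be tolerability score at the week 8 visit". Adherence, a secondary outcome, is also self-reported on a 0-100 scale.

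Section 2.7.A says that a prior study "observed a standard deviation of 15.1 for tolerability score", carries that SD over to each arm, and says the investigators "assume 7 evaluable subjects in each arm". From these it gives a 95% interval length of about 22.4, illustrated at a mean of 80 (68.8 to 91.2). A mean below 80 counts as substantial intolerance and is a reason not to proceed to UH3.

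Section 8.1 plans the "mean tolerability score at 8 weeks within each treatment group along with 95% confidence intervals (CIs"). It names no interval method for continuous scores; exact binomial intervals are specified for binary variables only. "If the data are skewed, transformations will be performed (e.g., log transformation"), and the median is reported if no suitable transformation is found. The plan anticipates a mean of at least 80, citing a prior low-dose naltrexone study "which reported tolerability scores of 89 in both intervention and placebo".

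**The concern.** A mean of 89 with SD 15.1 leaves only 11 points, or 11/15.1 = 0.73 SD, between the mean and the ceiling. Scores cannot spread upward as far as downward, so near that mean skewness is the expected case and not a remote contingency. Section 2.7.A does not show this, because its only illustration is at 80.

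Two things are at stake. First, the interval that accompanies the primary result may have less than its stated confidence, with errors that make tolerability look better established than it is. Second, both responses to skew in 8.1 move away from the arithmetic mean, which is the quantity compared with 80. Back-transforming a mean of logs gives a geometric mean, which is never above the arithmetic mean. Under left skew the median usually lies above the mean. The summary reported could therefore depend on a choice made after seeing the data, and would not be the one the progression rule uses.

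**Working it through.** **Inputs.** Cap 100 (2.2). SD 15.1 and 7 evaluable per arm (2.7.A). Means of 80 (illustration in 2.7.A) and 89 (prior study cited in 8.1). The documents do not give the shape of the score distribution, so every shape below is an assumption.

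**1. The plan's figure.** SE = 15.1/√7 = 5.71. Length = 2 × 1.96 × 5.71 = 22.4; at a mean of 80 the limits are 68.8 to 91.2. This reproduces 2.7.A and shows that it uses the normal multiplier with the SD treated as known. With t on 6 degrees of freedom (2.447) the length is 27.9.

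**2. The same interval at 89.** Normal multiplier: 89 ± 11.2 = 77.8 to 100.2. With t: 89 ± 14.0 = 75.0 to 103.0. Both pass the cap.

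**3. Left skew without assuming a shape.** A score capped at 100 and symmetric about 89 lies within 78 to 100, so its SD is at most 11. More generally, if the cap is d above the mean and the SD is s, skewness cannot exceed d/s - s/d. With d = 11 and s = 15.1 this is 0.728 - 1.373 = -0.64.

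**4. Coverage of the t interval.** True mean 89, SD 15.1, n = 7; 300,000 simulated samples per shape, with the two-point case computed exactly:

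| Assumed shape on 0-100 | Coverage | Upper limit above 100 |
|---|---|---|
| Scaled beta | 85.3% | 68% |
| Normal censored at 0 and 100 | 88.6% | 76% |
| 100 minus gamma | 84.9% | 56% |
| Mass at 100 plus uniform | 89.6% | 78% |
| Beta rounded to fives | 85.7% | 72% |
| Two-point (extreme case) | 94.1% | 75% |

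The misses are one-sided. Under the beta shape the lower limit lies above the true mean in 14.4% of samples and the upper limit lies below it in 0.2%; the nominal figure is 2.5% each. Under the censored normal the figures are 10.8% and under 0.5%.

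At n = 8 (first four shapes) coverage is 85.5-90.5%, and the upper limit passes 100 in 44-70% of samples. At a true mean of 80 with n = 7, coverage is 91.5-94.1%, and the upper limit passes 100 in 4-13%.

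**5. Effect of log.** Log is concave, so it cannot reduce left skew. Population skewness moves from -1.95 to -3.26 (beta), from -1.50 to -2.95 (censored normal) and from -1.05 to -1.22 (mass plus uniform). In the beta simulation log made skewness more negative in every sample of 7. It is undefined at 0, a score the scale allows.

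**6. The median.** With a true mean of 89, the population median is about 96 (beta) or 98 (censored normal), 7 to 9 points higher.

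**7. Alternatives tried.** A reflected log, log(101 - score), analysed by t and back-transformed under the beta shape, averaged 94.7 for a true mean of 89 and covered it in 76% of samples. A studentized bootstrap limited to 0-100 covered 93% (beta) and 90-91% (censored normal), but its lower limit fell to exactly 0 in 14% and 8% of trials.

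**The case against.** The strongest reply is that 8.1 does not commit to log. Log is only an example, and the plan goes to the median when no suitable transformation exists. A reader might infer from the text that the primary analysis will be a log-scale mean; the documents do not say so. That stands. But the only transformation named is one that cannot suit these scores, and the fallback comes without an interval method for the median and without a link to the mean-below-80 rule.

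A reader might also infer that the plan's own expected mean gives an interval with 85-89% coverage. The plan expects at least 80; 89 is a prior result for low-dose naltrexone, not nalmefene. Section 3.3 also records that enrolment into one arm stopped over tolerability concerns, which makes 89 doubtful for that arm. At 80 the shortfall is small. Coverage also depends on shape, as the two-point case shows, and on method: normal-multiplier intervals using the sample SD cover only 80-86% at n = 7 and a mean of 89, but pass 100 less often (27-54%, first four shapes). The point therefore holds only conditionally on a mean near 89.

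A third tempting reading is that poor coverage would corrupt the decision to proceed. It would not do so directly. The rule in 2.7.A uses the point mean together with a qualitative reading of discontinuation, adherence, side effects and willingness to continue. No confidence limit enters it, and no formal testing is planned. Section 8.1 also promises descriptive statistics and graphs, which partly serve the purpose of listing the scores.

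**Conclusion.** The point holds conditionally. If the week-8 mean is near 89 with SD 15.1, left skew is certain in the underlying distribution (skewness at most about -0.64); this rests only on the cap, the mean and the SD. The size of the coverage loss rests on assumed shapes: roughly 85-90% for plausible ones at n = 7, with misses almost all in the favourable direction and an upper limit above 100 in 56-78% of samples. At a mean of 80 coverage is about 92-94%.

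That log is the wrong example for these scores does not depend on the assumed shape, given left skew. The same reasoning applies to self-reported adherence if it too clusters near 100, although the documents give no mean or SD for it.

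The consequence lies in how the primary interval is read and which summary is reported. It does not reach an error rate or the stated progression rule itself.

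**What to change.** In 8.1:

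- Remove log transformation for the 0-100 tolerability and adherence scores.
- Always report the untransformed week-8 mean, since that is the quantity in the mean-below-80 rule, with a t-based 95% interval limited to 0-100. Describe it as approximate and likely to under-cover near the ceiling. Limiting it leaves coverage unchanged, because the true mean cannot lie outside 0-100.
- Add the median and range as supplements, not replacements, and list all individual scores by arm. With at most 8 per arm the list is short and needs no distributional assumption.

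In 2.7.A, add the interval at a mean of 89 (75.0 to 103.0 with t) and note that it passes the cap.

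A back-transformed reflected log should not be used to estimate the mean, and a studentized bootstrap need not be required; step 7 of the working shows why.

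The cost is a few lines of wording and code. The downside is a wider, less favourable stated interval: at 89, limited to the scale, 75.0 to 100 has length 25.0, against 22.4 in the plan.

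### Does the skewness rule in section 8.1 leave open which week 8 tolerability figure is compared with 80?

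*Combined protocol and SAP*

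**What the plan says.** Section 2.2 makes the week 8 score on a 0-100 visual analog scale the primary outcome.

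Section 2.7.A sets the rule for not moving on to UH3. One ground is "mean tolerability rated < 80". The other, joined by and/or, applies "if other results qualitatively suggest intolerance", and it covers discontinuation, non-adherence, side effects and unwillingness to continue. The same section rules out formal testing and gives the precision expected with 7 evaluable participants per arm.

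Section 8.1 has three relevant sentences. The planned summary is stated without condition: "We will report descriptives such as mean tolerability score at 8 weeks within each treatment group", with 95% CIs. A little later comes "If the data are skewed, transformations will be performed (e.g., log transformation) or the median will be reported if no appropriate transformation is identified". The next sentence returns to the mean: "We anticipate that mean tolerability" scores will not fall below 80.

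No sentence links the skewness rule to the threshold in either direction.

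**The concern.** The skewness sentence stands between two sentences about the tolerability mean, so it applies to that outcome. Skew is also plausible. Section 2.7.A says an earlier study "observed a standard deviation of 15.1 for tolerability score", and section 8.1 refers to a prior study "which reported tolerability scores of 89 in both intervention and placebo". Taken together, these put the ceiling of 100 less than one SD above the mean.

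The one transformation named, a log, makes left skew worse and is undefined at a score of 0. An analyst might therefore turn to a reflected log or to the median. Both tend to lie above the arithmetic mean in left-skewed data, and both give less weight to the low scores that signal intolerance. Neither the word for skewed nor the word for appropriate has a cut-off.

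If such a substitute replaced the mean in the comparison with 80, an arm with a mean below 80 could appear to pass, and the choice could be made after the data were seen.

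**Working it through.** **The plan's own figure.** With SD 15.1 and n = 7 (section 2.7.A), the CI length is 2 × 1.96 × 15.1/√7 = 22.4, or 68.8 to 91.2 around a mean of 80. This matches the document. The t quantile on 6 df gives 27.9.

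**How likely is skew?** (100 − 89)/15.1 = 0.73 SD from mean to ceiling. A beta shape with mean 89 and SD 15.1 (the shape is an assumption) has skewness −1.95. At a mean of 80 it is −0.99.

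**How far can the summaries differ?** Take seven assumed scores with the plan's SD: 95, 90, 85, 85, 80, 70, 50.

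| Summary | Value | Side of 80 |
|---|---|---|
| Mean, 555/7 | 79.3 | below |
| Median | 85 | above |
| Back-transformed log(101 − x) | 83.2 | above |
| Back-transformed plain log (geometric mean) | 77.8 | below |

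Skewness is −1.4 on the raw scale, −1.7 after a plain log and about 0 after the reflected log. The t-based 95% CI for the mean is 79.3 ± 2.447 × 15.1/√7, or 65.3 to 93.3.

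**How often would a substitute disagree with the mean?** The assumptions are beta-shaped scores, SD 15.1, n = 7 and 400,000 arms per scenario. The analyst switches when bias-corrected skewness is below −1, then uses log(101 − x) if that brings skewness within 1 of zero and otherwise uses the median. The plan contains none of these switching rules.

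| True mean | Arms that switch | Mean < 80 but substitute ≥ 80 | of which median |
|---|---|---|---|
| 75 | 23% | 7.5% | 1.3% |
| 78 | 28% | 8.8% | 1.3% |
| 80 | 32% | 8.5% | 1.1% |
| 85 | 47% | 5.1% | 0.5% |
| 89 | 67% | 2.8% | 0.2% |

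Moving only the cut-off changes the third column at means of 75 to 80 to about 3% (cut-off 1.5) or 14-16% (cut-off 0.5). Under the sequence above the opposite conflict is below 0.01%. If the plain log is used in the same switched arms, a mean at or above 80 with a substitute below 80 occurs in 1.8% of arms at a true mean of 75, 4.2% at 80 and 5.6-5.7% at 89.

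**What do the conflicts amount to?** In every simulated conflict under the sequential rule, the 95% CI of the raw mean contained 80. For the median this holds by algebra. With seven scores the median exceeds the mean by most, relative to the SD, when four scores are equal and three lie lower by d. The gap is then 3d/7 = 0.429d, the SD is √[(12/7)d²/6] = 0.535d, and the ratio is 0.80. The t half-width is 2.447/√7 = 0.925 SD. So if the mean is below 80 and the median is at or above it, the interval must reach 80.

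**Does the text permit the substitution?** Section 2.7.A names the mean and nothing else. Section 8.1 commits to the mean without a skew condition. Its skewness sentence says that a median will be reported, but not that it replaces the mean, and it mentions neither 80 nor UH3. Section 8 separately calls for descriptive statistics at every follow-up time, and section 8.1 for graphs of all outcomes. A report that followed these sections would contain the raw mean of the seven or eight scores.

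**The case for a change.** The strongest opposing case is that a plan should not leave its only numeric go/no-go figure to inference, least of all in the skewed case that its own inputs make plausible. The decision rests on a descriptive number, so the absence of formal testing is no answer. Arm B continues to its target of 8 (section 3.3), so the week 8 summary still matters there. Among simulated arms that switch and have a mean below 80, the reflected-log or median summary lies at or above 80 in about 44%, 61% and 71% at true means of 75, 78 and 80. One sentence would remove the doubt.

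Parts of this stand. The skewed case is not spelled out, and a plain log is a poor example for a score crowded near its ceiling.

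The rest is weaker. The percentages come from rules that the plan does not contain, and most of the conflict comes from a reflected log that it never mentions. The median accounts for only 1.1-1.3% of arms at means of 75 to 80. The direction of error is not fixed either, since the one named transformation moves the result downward. Skew is also not the usual case where conflict is most frequent: at means of 75 to 80 the assumed trigger fires in 23-32% of arms. It fires in most arms only at 89, where conflict is 2.8%. The documents do not say that 89 and 15.1 come from the same sample, and the plan's own expectation is only a mean of at least 80.

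**Conclusion.** No change follows. The decision figure is already fixed by section 2.7.A as the mean, and section 8.1 plans to report that mean. The skewness sentence governs additional description and does not amend the threshold. An analyst working from the text would hold the raw mean against 80 and show a median or transformed summary beside it. What is missing is a cross-reference that would do no harm but would not alter the decision.

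Barring the median for this outcome, as a stricter rule would, is a matter of preference. With seven scores the mean is sensitive to one participant: in the example, dropping the score of 50 moves it from 79.3 to 505/6 = 84.2. A median alongside is useful for that reason.

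The practical effect is small even if the text were misread. Conflicts arise only where the raw mean is too imprecise to be told apart from 80, and section 2.7.A already shows an interval about 22 points wide. The no-go decision also has qualitative grounds, and section 3.3 records that enrollment into arm A was stopped over tolerability without waiting for a week 8 summary. The simulated rates rest on an assumed beta shape, the plan's SD, n = 7 and assumed switching rules, so they illustrate the range and are not estimates of how often the trial would go wrong.
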